Prevalence Rates and Consequences. Epidemiological trends indicate an increase in PSM misuse among young adults and college students, and rates are at their highest level in 15 years, which poses a growing public health concern^{20, 21, 23, 181}. Estimated prevalence rates vary widely; in over 25 studies of college student PSM misuse conducted through 2009¹⁸⁰, estimates ranged from a low of 5.9% for past 30 days, to a high of 36% for lifetime prevalence in a general sample and 55% for lifetime rate in a fraternity sample^{4, 24, 27, 28, 180}. Our own work has revealed that, by the fourth year of college, at least 31% of students have engaged in PSM misuse at least once in their lifetime, and annual prevalence peaks during the third year of college at approximately 20%¹. In addition to rising prevalence rates, there are many consequences of PSM: headaches (33% of users), stomachaches (33%), irritability (62%), sad mood (25%), and sleeping difficulties (72%)^{4, 29}. PSM misuse has also been associated with health issues including cardiovascular failure, jitteriness, hyperthermia, seizures, and anxiety^{12, 186}. Compared to students who do not, those who misused PSM also had more social difficulties, had lower GPA, and reported concerns about their academic performance²⁹⁻³¹. Our research has also found students who misuse PSM skip classes more frequently and spend less time studying than those who do not use or who use only as prescribed^{27, 147}.

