1) ***Misuse of Prescription Stimulant Medication.*** For the past decade, [name] has led the NIDA-funded College Life Study (CLS), which included over 1250 young adults originally enrolled as college students. She has focused on understanding the antecedents and consequences of all forms of substance use during college, and in particular on PSM. Her team has numerous publications^{1, 27, 41, 145-149, 159, 174, 178} on the risk factors for PSM misuse and longitudinal interrelationships between PSM misuse and other forms of drug use, and academic variables. Two recent studies at UW have also included items regarding PSM misuse. In the first (R01AA012547; [name] PI, [name], [name] Co-Is, [name] collaborator), a random sample of 1477 students completed a web survey of stimulant use, of whom 3.8% reported misuse of their own PSM and 9.8% reported misuse of another's PSM in the past year. In the second study, [name] and colleagues completed a survey of lifetime use among students 18-25 and found that 19% reported PSM misuse. Results also support a need to correct misperceptions; despite 81% having never used PSM, 89% believed the typical student had used for non-medical reasons at least once¹⁵⁶. Drs. [name], [name], and [name] have also recently begun (July 2014) a collaborative project with the National Association of Student Personnel Administrators (NASPA) to better understand trends, perceptions, motives, and effects related to PSM misuse. The UW team will lead a 9 campus initiative to develop and conduct surveys and in-person focus groups with students and administrators to explore implications for prevention campaigns and make suggestions for intervention development – information from this project will undoubtedly set the stage for even greater success with the proposed research.

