4) Perceived norms and AOD as theoretical mediators: We have completed 5 RCTs evaluating efficacy of computer/internet delivered PNF for alcohol use among college students^{93-95,142}. Consistent with our proposed research hypotheses, drinking reductions in all studies were mediated by changes in perceived norms for the typical student, providing additional support for the correction of normative misperceptions as an active theoretical mechanism for intervention efficacy. [name] and colleagues¹⁴³ also investigated the impact of norm misperception on illicit drug use. 5990 participants provided information on use, perceptions, and consequences of marijuana use. Two-thirds of participants reported no marijuana use, but 98% of respondents incorrectly predicted the "typical student" used marijuana at least once per year. Estimates of peer use and use by the typical student each added significantly to separate equations predicting variance in drug use and in related consequences. [name] has collected preliminary data at UAlbany supporting misperceptions of the norm for PSM misuse. Specifically, students were asked "Within the last school year, do you think the typical student at your school used any of the following prescription drugs (for stimulants) that were not prescribed to him/ her?" Results indicated 74% of students perceived that the typical student used stimulants within the last year, though the actual rate of use on that campus was reported at 25%. Drs. [name] and [name] recently published a paper on normative misperceptions of PSM¹⁵⁶. Their research similarly found that students overestimated PSM misuse by other students and those normative estimates were associated with student's own higher PSM use. Living in a fraternity or sorority was related to higher PSM use and perceived norms. Finally, higher normative perceptions were associated with higher hazardous drinking. Thus, our preliminary studies and bio-sketches demonstrate our ability to successfully conduct this research.

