Study Methodology Overview: The proposed RCT aims to examine the efficacy of a PFI for reducing PSM misuse. Study 1 will document normative perceptions on each of the 3 participating campuses. Study 2 will examine the efficacy of a web-delivered PFI adapted and expanded from models like BASICS which will contain tailored information on normative misperceptions of PSM misuse, contrasting commonly held misconceptions about the benefits of PSM with research-based information about the actual effects of PSM, and learning and study strategies as alternatives to PSM misuse compared to a control condition, as well as components targeting comorbid alcohol and marijuana misuse. For Study 3, an in-person individually-delivered PFI (adapted from web format to face-to-face) addressing PSM and AOD misuse will be compared to the web-delivered PFI tested in Study 2 and to an assessment only control. The two studies will evaluate outcomes with respect to both short-term (6 months) and longer-term (12 and 18 months) reductions in four substance-related outcomes: (a) the perceived norms and benefits of PSM misuse, (b) PSM misuse frequency, (c) marijuana use frequency, and (d) alcohol use frequency and quantity.

Setting: Participants will be recruited from three universities: The University of Washington (UW), the University of Maryland College Park (UMCP), and University at Albany, State University of New York (UAlbany). UW is located in Seattle, WA and UMCP is located nine miles from Washington DC, with each school's total undergraduate enrollment of more than 30,000. UAlbany, which is one of four SUNY University Centers, is classified as a Research II and NCAA Division I institution with more than 12,000 undergraduate students. All three universities are coeducational and very diverse with regard to race, ethnicity, religion, gender, age, disability, and sexual orientation.

Studies 1 & 2 Recruitment Procedures: A total of 8,172 undergraduates for Study 1 and 15,732 for Study 2 aged 18 to 24 (age restricted in order to maintain comparability with prior SBI/PFI interventions with college students) will be randomly selected from the University Registrars' databases across the 3 sites. Students will be emailed an invitation to log on to a secure web browser, read a consent statement and indicate their willingness to participate in the study. Approximately 50% of invited students will respond to the invitation (Study 1 N=4,086 and Study 2 N=7,866).

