Studies 1 & 2 Screening for Eligibility: For *Study 1*, all students randomly selected from the registrars' databases will be eligible to complete a 30-minute survey via a secure server, regarding PSM use, PSM misuse, normative perceptions, AOD use, and other relevant constructs. Participants will be paid \$20 for completing the survey. Following completion of *Study 1*, we will select and invite focus group participants at UW to get subjective impressions of and suggestions surrounding feedback components and modules drafted for the purposes of this application (see Appendix B). We will conduct 5 focus groups of 8-10 individuals at the UW involving *Study 1* participants who indicate willingness to participate and who have used PSM in the past. We will use focus groups in an iterative fashion and provide intervention refinement following feedback elicited about the treatment materials. We will then conduct an additional 2-3 focus groups for final reactions and input to the PFI intervention. Investigators will then meet to decide what changes (if any) should be made to the intervention prior to implementing the PFI for *Study 2*, based on transcripts and detailed notes taken during the focus groups and the consistency of participant feedback regarding various components. Groups will be conducted in person, led by two interviewers, and recorded. The primary interviewer will guide discussion through open-ended questions, while the secondary interviewer takes notes and observes responses. For *Study 2*, eligibility will be determined based on a brief web-based, self-administered screening questionnaire. Screening items will assess PSM use, PSM misuse, consequences, alcohol, marijuana, and other drug use. There are two main eligibility criteria for *Study 2*. First, to allow for studying academic outcomes, participants must be undergraduate students in their second semester or later at the university, have an anticipated graduation date at least 18 months in the future, and be planning to remain at their home university for at least 18 months. Second, to study possible reductions in PSM misuse but to include all students who maybe engaging in risky behaviors, participants must have engaged in PSM misuse once or more in the past month and/or 6 or more times in the past year. Based on prior studies^{4, 24, 27, 28, 112, 156}, we expect 14%-20% will meet criteria for PSM misuse and agree to participate. Students will be paid \$10 for completing screening for *Study 2*. Up to six reminders to participate will be emailed¹¹¹. The IRB at each institution will approve all procedures.

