Power. Because count outcomes will typically require a larger sample size to detect effects than continuous outcomes, we assess power for the GLMMs for PSM use. Thus, power estimates for the GLMM will be conservative for the linear mixed models. For Aim 2, we are not aware of power analysis software to estimate power for GLMMs; thus, we used a simulation-based approach. Simulations based on models that contain “true” effects can provide an estimate of power. Two-hundred datasets were generated based on the model in equation 1 where estimates for fixed and random-effects were guided by previously collected data of similar interventions for reducing problem alcohol use and the existing literature. The GLMM model was fit to each dataset and specific output were saved (e.g., regression coefficients, *p*-values). The percentage of datasets with statistically significant effects (i.e., $p < .05$) for a given hypothesis provides a simulation-based estimate of power for this hypothesis. A number of simulation runs were conducted varying the size of the fixed-effects. These simulations revealed a sample size of 600 per treatment condition will yield power > 0.80 given the magnitude of the treatment \times time-dummy interaction coefficient was $-.13$ or smaller. Assuming no baseline differences in the outcome, this would correspond to a rate ratio of $.87$ at a given follow-up time point (i.e., a 13% decrease in PSM use for PNF intervention compared to control). Given our power to detect fairly small effects of the Aim 2 intervention, we would expect reasonable power to detect mediated and moderated effects as well. For Study 3 planned analyses of the web-based and in-person interventions, we also ran similar sets of simulations to assess power for varying effect sizes. We used similar estimates of random effects, but allowed the fixed effect of the intercept to be higher given the high risk sample and we specified a sample size of 100 per arm (300 total). Based on the simulations, we would expect power of $.80$ or higher to detect coefficients $-.3$ or smaller which corresponds to a RR of $.74$.

Timeline:

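### Study 2's 14%-20% yield is not supported for the misuse rule actually used, so the plan's own figures do not secure 1,200 participants

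*Combined protocol and SAP*

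**What the plan says.** **Draw and response** (Studies 1 & 2 Recruitment Procedures): "A total of 8,172 undergraduates for Study 1 and 15,732 for Study 2 aged 18 to 24" are to be sampled from registrar lists. "Approximately 50% of invited students will respond to the invitation (Study 1 N=4,086 and Study 2 N=7,866").

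**Misuse rule and yield** (Studies 1 & 2 Screening for Eligibility): "participants must have engaged in PSM misuse once or more in the past month and/or 6 or more times in the past year". Later in the same section: "we expect 14%-20% will meet criteria for PSM misuse and agree to participate". Six references are cited for this range. The text does not say which time window they used or what agreement rate is assumed.

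**Prevalence figures elsewhere:**
- Prevalence Rates and Consequences, from the team's own work with no campus named: "annual prevalence peaks during the third year of college at approximately 20" percent.
- Preliminary/Pilot Studies, item 1, a random sample at UW asked about the past year: "of whom 3.8% reported misuse of their own PSM and 9.8% reported misuse of" another person's.
- Preliminary/Pilot Studies, item 4, for UAlbany: "the actual rate of use on that campus was reported at 25" percent. The survey item quoted there concerns the last school year and stimulants not prescribed to the student.

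**Target** (Power): "a sample size of 600 per treatment condition will yield power > 0.80" at a treatment-by-time coefficient of -.13. Aim 2 gives the total as 1,200 people.

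**The concern.** Everyone who satisfies the misuse rule is a past-year misuser, but not every past-year misuser satisfies the rule. A student with a few episodes in the year and none in the last month is excluded. The share who meet the rule and also agree must therefore be no larger than the past-year rate. Yet the range given for that share is about the size of the documents' figures for any misuse over a year. At UW its low end lies above the past-year bound.

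The documents describe use as clustered around mid-terms and finals, which adds to the doubt about how many past-year misusers would qualify.

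The Study 2 power statement depends on reaching 600 per arm. If the yield is lower than assumed, the draw of 15,732 produces a smaller trial, and the effect it can detect is larger than the one stated.

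**Working it through.** **1. Reproduce the plan's recruitment figure.** 15,732 × 0.50 = 7,866, as stated. There is no arithmetic error here.

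**2. Yield needed.** 1,200 / 7,866 = 15.26%, about 15.3%.

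**3. Yield stated.** 7,866 × 0.14 = 1,101 and 7,866 × 0.20 = 1,573. The range straddles 1,200, and its low end is 1,200 - 1,101 = 99 short.

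**4. Compare with the documents' rates over a year.**
- UW: 3.8% + 9.8% = 13.6% if nobody is in both groups, less if some are. This is below both 14% and 15.3%. Applied to all sites, 7,866 × 0.136 = 1,070, even if every past-year misuser met the rule and agreed.
- Third-year peak of 20%: 15.26 / 20 = 76% of past-year misusers would have to meet the rule and agree.
- UAlbany 25%: 15.26 / 25 = 61%. This item leaves out misuse of a student's own prescription, so past-year misuse as the plan defines it could be higher there and the needed share lower.

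The yield sentence does not mention the separate academic-standing and graduation criterion, which could lower the count further.

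**5. Approximate power.** The simulation's baseline rate and random-effect variance are not given, so it cannot be rerun. Instead I assume power of exactly .80 at 600 per arm, two-sided α = .05, and a standard error proportional to 1/√n:
- SE at 600 = .13 / (1.960 + 0.842) = .0464
- power(n) = Φ(2.802 × √(n/600) - 1.960)
- coefficient detectable with 80% power = .13 × √(600/n), and the detectable rate ratio (RR) = exp(-coefficient)

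For a 14% yield, n = 1,101/2 ≈ 551, so power = Φ(2.802 × .958 - 1.960) = Φ(.724) ≈ .77.

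| Yield | Total N | Per arm | Approx. power at -.13 | Approx. detectable RR |
|---|---|---|---|---|
| 8% | 629 | 315 | .53 | .836 |
| 10% | 787 | 393 | .62 | .852 |
| 12% | 944 | 472 | .70 | .864 |
| 13.6% (UW upper bound) | 1,070 | 535 | .75 | .871 |
| 14% (plan's low end) | 1,101 | 551 | .77 | .873 |
| 15.3% (break-even) | 1,200 | 600 | .80 | .878 |
| 17% (plan's midpoint) | 1,337 | 669 | .84 | .884 |
| 20% (plan's high end) | 1,573 | 787 | .89 | .893 |

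The 8%, 10% and 12% rows are illustrative and are not rates from the documents. The plan prints RR .87 for -.13, whereas exp(-.13) = .878.

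**The case against.** The best defence is that the plan presents 14%-20% as the yield for the criteria it has just defined, backed by sources that cannot be inspected here. Taken at face value, any yield from 15.3% to 20%, which is most of the range, reaches 1,200. The 17% midpoint even leaves room for the expected 90% retention (1,337 × 0.90 = 1,203), although the plan does not say it was sized that way. Exam periods recur every term, so clustered use can still add up to six episodes a year, and screening near a peak would catch past-month use. The plan also claims power above .80, not equal to it. If power were .85 at 600, a 14% yield would still give about .82.

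All of this stands, and it rules out several stronger readings that a reader might infer:
- *The range was copied from past-year prevalence.* The sizes are similar, but the text does not state the window behind the figure.
- *The three rates average to a ceiling near 19.5%, so 78% of past-year misusers must qualify.* That needs equal site shares, which are not stated. It also assigns the 20% figure to the third campus, which the text does not do. And it treats the UAlbany item as complete, which it is not.
- *The yield is really the 5.9% past-30-day rate.* That is the lowest estimate quoted, and it omits students with six or more uses in the year but none in the last month.
- *The power claim is wrong.* It is conditional on 600 per arm, and a doubt about recruitment does not refute it.

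None of this supplies a rate for the actual rule or an agreement rate. Nor does it change the fact that the low end of the plan's own range misses the target. Limitations of the Proposed Research acknowledges a possible small sample, but answers with the 50% contact rate and does not discuss eligibility.

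**Conclusion.** The concern holds as a planning assumption that lacks support. The 1,200 target is not secured by the plan's own range and figures: 14% gives 1,101 (power about .77), and UW's past-year upper bound applied to all sites gives 1,070 (about .75). Against the stated range alone the loss is modest, with the detectable rate ratio moving from about .878 to .873. It grows if the true yield is nearer 10%, where N is about 787, power about .62 and the detectable rate ratio about .85.

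A shortfall is possible but not proven, because the rate under the rule is unknown.

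The subset argument and the head counts need no assumption beyond the plan's 50% response. The powers assume exactly .80 at 600, a two-sided test and simple scaling with sample size, so they are approximations and would be higher if the simulated power at 600 was well above .80.

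**What to change.** Before Study 2 invitations go out:
1. Tabulate from the Study 1 survey, overall and by campus, the proportion who meet the actual misuse rule. About 4,086 students on the same three campuses are expected. At a rate of 12%, the 95% margin is 1.96 × √(.12 × .88 / 4,086) ≈ 1.0 percentage point, enough to tell 12% from 15.3%. The Study 1 items need to capture both past-month misuse and the past-year count.
2. Replace 14%-20% with that proportion and state the assumed agreement rate separately, since Study 1 does not supply it.
3. In the Power section, restate the expected N and detectable rate ratio at that yield and at lower ones, for example 8%, 10%, 12% and 14%. Label the powers as approximations unless the simulation is rerun with its inputs reported.

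The cost is one tabulation of data already being collected, a revised paragraph, and a stated detectable effect that may look less favourable. Enlarging the email draw is optional. At $10 per completed screen, holding 1,200 would add about $7,060 at a 14% yield (1,200/.14 ≈ 8,572 screens, 706 more than 7,866) and $41,340 at 10% (12,000 screens, 4,134 more).

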Study 3 Recruitment, Randomization & Assessment Procedures: All students who present for services at the University at Albany Health Center and University Counseling Center will be invited to complete a brief, web-based assessment of their PSM and AOD (identical to *Study 2*) in order to assess eligibility for *Study 3* before meeting with their service provider. Routine screening is already part of ordinary clinical practice at UAlbany Health and Counseling Centers, and annually more than 1300 unique individuals visit these centers and complete routine screening. Our own pilot data suggests more than 2/3 of heavy illicit substance users make at least one visit to a campus health clinic annually, indicating these settings are ideal for identifying non-treatment-seeking at-risk PSM users. During the student's medical or counseling appointment, the provider will review the Screening Questionnaire and will refer eligible students to the study using a referral script similar to ones from prior studies successfully conducted in this setting. The same eligibility criteria will be used: students must have misused PSM once or more in the past month and/or 6 or more times in past year.

Students agreeing to participate in the study will be emailed an invitation to log onto a secure web browser,

read a consent statement and indicate their willingness to participate in the study. Those indicating their consent will immediately be routed to the baseline survey which will be used to generate the web-delivered or in-person PFI content and for which they will receive \$20. Following baseline, participants will be randomly assigned to one of three conditions (n = 100 per condition). For Study 3, students will be randomly assigned to either a web-delivered PFI (as in Study 2), a one-session face-to-face brief intervention delivered in an MI style using the PFI as generated in the web condition, or an assessment only control group.

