Participants will complete a battery of web-based follow-up assessments at 6, 12, and 18 months post-baseline for which they will receive \$20, \$25, and \$30, respectively. Participants will additionally complete a brief post-intervention assessment of satisfaction with services and convenience of the intervention, and at each assessment they will be asked whether they have sought other drug treatment since the intervention to control for possible confounding treatment effects. These data will help determine the ideal interventions for the service delivery settings in regard to ease of access and utilization by participants.

Study 3 Training and Ongoing Supervision of Interventionist: One potential method for maintaining or enhancing the efficacy of individual brief interventions for college students seeking campus health and mental health care beyond the life of a research project is to train and supervise existing service providers to deliver the feedback interviews. The current approach will provide training to enhance existing knowledge of the UAlbany Counseling and Health Center staff regarding PSM misuse, and will utilize an existing provider imbedded in the Counseling Center staff at UAlbany to provide the in-person interventions. The provider will complete specific additional training related to both the MI process and PSM, alcohol, and marijuana content of the proposed intervention, and will participate in weekly supervision meetings with Drs. [name] and [name]. In addition, all intervention sessions will be audio-recorded and reviewed for adherence to the protocol and MI competence using existing protocols developed for use in prior funded projects at UAlbany and UW. The interventionist will also complete an adherence checklist after each individual session, to indicate which components were covered in each intervention session. Scores on adherence/competence measures and checklists will be reviewed and included as a covariate in secondary analyses of intervention efficacy.

Measurement and Assessment Procedures: Measures will be completed via a secure web survey, using DatStat Illume and will last 30-45 minutes. Measures selected are in Appendix A.

PSM Measures		
PSM Use	DV	
 PSM Timeline Followback (TLFB) - Quantity and past-30-day frequency of PSM misuse¹⁸⁸ Medical Use, Medical Misuse, and Non-Medical Use Questionnaire^{23, 80}

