PSM Consequences	DV	
 Drug Abuse Screening Test (DAST)³² The CAGE Questionnaire – Stimulant Use¹⁸⁹ Prescription Stimulant Use Consequences⁴
PSM Motivations	Moderator	
 Prescription Stimulant Use Motives Questionnaire⁹¹ Motives for Not Using⁹
PSM Norms and Attitudes	Mediator	
 Prescription Stimulant Norms Rating Form⁷⁴ Attitudes about PSM and Diversion⁴ Prescription Stimulants Expectancy Questionnaire (PSEQ-II)¹⁸⁷
AOD Measures		
AOD Use	DV/Mediator	
 Quantity/Frequency/Peak Alcohol Use Index^b Daily Drinking Questionnaire¹¹³ Alcohol and Marijuana Timeline Followback (TLFB)^{9,10} - Quantity and past-30-day frequency of marijuana and alcohol use, (use days, heavy episodic drinking, and typical and peak BAC ASSIST¹³² - Other drug use
AOD Consequences	DV	
 Rutgers Alcohol Problem Index (RAPI)¹⁹¹ Rutger's Marijuana Problem Index (RMPI)^{169,192,193}
Reasons for Not Using	Moderator	
 Attributions for Limiting or Abstaining from Illicit Drugs (ALAID)⁹
Other Measures		
Demographic Characteristics	Covariate/ Moderators	
 Standard questions will be used to assess age, sex, sexual orientation, race/ethnicity, parental education level, number of hours per week working for pay, religiosity, and current living arrangement
Academic Characteristics, Skills and Outcomes	Feedback	
 Learning and Study Strategies Inventory, 2nd edition (LASSI)¹⁷⁵ Relapse Prevention/Protective Behaviors Scale¹⁹⁰ Satisfaction with Academic Progress and Skills Factors affecting Academic Performance Activities/Options that Could Improve Grades or Academic Progress

		
 ▪ Primary Academic Outcomes: GPA ▪ Academic Behaviors ▪ College Engagement¹⁹⁴
Satisfaction	Covariate	▪ Participants' satisfaction with interventions (assessed post intervention)

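### Study 3 adherence/competence scores exist only in the in-person arm, so using them as an ordinary efficacy covariate removes or redefines the comparison with control; satisfaction and later drug treatment are post-randomisation and should not adjust it either

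*Combined protocol and SAP*

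**What the plan says.** Study 3 randomises after baseline: "participants will be randomly assigned to one of three conditions (n = 100 per condition"). The arms are web-delivered feedback, one face-to-face session, "or an assessment only control group".

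The section on training and supervision of the interventionist says that "all intervention sessions will be audio-recorded and reviewed for adherence to the protocol and MI competence", and that "The interventionist will also complete an adherence checklist after each individual session". It then gives the rule at issue: "Scores on adherence/competence measures and checklists will be reviewed and included as a covariate in secondary analyses of intervention efficacy".

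The measures table (Measurement and Assessment Procedures, Other Measures) assigns the role of covariate to "Participants' satisfaction with interventions (assessed post intervention"). The Study 3 assessment procedures add that at each assessment participants will be asked "whether they have sought other drug treatment since the intervention to control for possible confounding treatment effects".

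The Aim 3 model in the Data Analysis section uses one indicator for web and one for in-person, with control as the reference. It has no term for adherence, satisfaction or other treatment. No section says how any of the three is coded for a participant who has no value, or which arms the adjusted analyses include.

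**The concern.** A covariate in a model that compares arms has to be defined for people in every arm. Adherence and competence describe a session, and neither web nor control participants have one. The rule therefore asks for something that an ordinary regression cannot do as written: the software either discards the people without a score, or the analyst has to invent a value for them. Either way, the result may be reported as adjusted efficacy when it is not the effect of the delivered intervention against control.

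The other two variables raise a different problem. Both are measured after assignment, so neither can confound a randomised comparison, and both may respond to assignment. Conditioning on them can remove part of the effect or bring in selection.

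**Working it through.** **Inputs.** Arm size and number of arms come from the Study 3 procedures. The Power section repeats them ("we specified a sample size of 100 per arm (300 total")) and gives a target coefficient of -.3, or RR .74. The model form is that of Aims 2 and 3.

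**The plan's own figures.** 3 × 100 = 300, and exp(-0.3) = 0.741; both agree with the text. The simulated power cannot be reproduced, because the intercept and random-effect variance are not given. It is not in dispute here.

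**Adherence, complete-case.** Let W and P be the web and in-person indicators and S the score. Take four columns: intercept, W, P, S. Only in-person participants have S, so the usable rows number at most 100 (fewer if some never attend), with 0 controls and 0 web participants. In those rows the intercept is always 1, W is always 0 and P is always 1. The intercept and P columns coincide and W is empty, so the rank is 2 of 4. No between-arm coefficient is estimable. The same holds in the repeated-measures form, where each P-by-visit column equals its visit column. The missing-data paragraph does not help: ignorability is an argument about values that could have been observed, not about a covariate undefined by design.

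**Adherence, zero-filled.** Replace S by P × S. The rank is now 4 of 4. With coefficients b_P and b_S, the in-person versus control contrast at score s is

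b_P + b_S × s,

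so b_P alone is the contrast at s = 0. To show what this can do, assume (these values are not in the documents) a mean score of 5 and a true contrast at that mean of -0.3, the plan's own target. Then b_P = -0.3 - 5 × b_S.
- If b_S = 0, b_P = -0.3 (RR 0.74).
- If b_S = -0.1, b_P = -0.3 + 0.5 = +0.2 (RR exp(0.2) = 1.22).

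A beneficial session would then be displayed as a harmful one, purely through coding.

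One qualification applies. This affects the plan's efficacy coefficients (arm by visit) if the score enters the visit-specific equations. If it enters the intercept equation only, the shift falls on the baseline arm difference and the arm-by-visit coefficients are the same under either coding. The plan does not say which is intended.

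**Adherence, centred.** Use P × (S - mean S in the in-person arm). The contrast at the mean score is now b_P itself, and all 300 participants stay in the model.

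**Satisfaction.** The measures table refers to satisfaction with interventions, after intervention. The Study 3 procedures ask participants, with no arm named, about services and about convenience of the intervention. Controls receive no intervention, but they were recruited when presenting for care and could rate services. Whether they have a value is unsettled. If they do, it rates something different from a web programme or a counselling session.

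**Other treatment.** The recall window starts at the intervention. Controls have no such date; a single session and modules spread over a term also start and end differently. The feedback includes campus resources for assessment and support (Prescription Stimulant Medication Misuse PFI), so assignment can plausibly change treatment seeking. No rate of treatment seeking is given by arm, so no bias can be computed.

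**The case against.** The strongest reply is that this is a small gap in specification. Adherence is confined to secondary analyses, and those words are compatible with a within-arm analysis. Satisfaction is tied to a model only by one word in a table, and the Study 3 text gives it a descriptive purpose: judging which intervention suits the setting. The Aim 2 and Aim 3 models contain none of these variables. All of this stands and limits the reach of the point. It does not remove it, because the text gives an instruction to include the scores as a covariate for efficacy, with no arm restriction or coding rule.

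Four stronger readings are tempting, and the documents do not support them.
- A reader might infer that a model with adherence cannot compare arms at all. It can, if the score is centred within the in-person arm.
- A reader might infer that satisfaction would remove every control from the analysis. The Study 3 procedures leave open that controls rate services.
- A reader might infer that Study 2 has no occasion for a satisfaction rating, because its procedures list only 6, 12 and 18 months after baseline. The Aim 2 model has five repeated measures including a post-intervention wave, so the text does not settle this.
- A reader might infer a material bias from adjusting for later treatment. Study 2 controls also receive referrals, and students indicating significant dependence are contacted and referred with no arm restriction, so even the difference between arms is uncertain.

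**Conclusion.** The concern holds for the covariate-adjusted analyses and not for the main comparisons. For adherence/competence the conclusion follows from the design: at most 100 of 300 participants, in one arm, under complete-case handling; or, with zero-filling in the visit-specific terms, a coefficient that refers to zero adherence. The +0.2 example rests on an assumed mean score and slope and shows only that the sign can change.

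For satisfaction and other treatment the conclusion is one of principle: both are post-randomisation, neither is clearly defined for controls, and adjustment does not give the randomised effect. Its size cannot be derived from the documents. This should be corrected before the secondary analyses are run. It does not call the primary models into question.

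**What to change.** Replace the covariate rule with three statements.

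1. Relate adherence/competence to outcome within the in-person arm only, labelled as a non-randomised, within-arm association. If the score is kept in the three-arm model, enter it as in-person indicator × (score minus in-person mean) in each follow-up equation, so that the arm coefficients are read at average adherence.
2. Report satisfaction by arm, state which arms are asked and what they rate, and remove its covariate role from the efficacy models.
3. Ask about other drug treatment over the same window in all arms, for example since the last survey. Report it by arm, and do not adjust the randomised comparison for it.

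The cost is SAP wording and one reworded survey item. No randomised comparison is lost.
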